In order to improve the implementation of prehabilitation, we have, on the one hand, streamlined the content of prehabilitation, improved the implementation process, and published a prehabilitation guideline in our previous prehabilitation research; on the other hand, we hope to explore a more feasible management model. Multidisciplinary collaboration is the foundation of prehabilitation.

“Internet+medical service” has become a new mode of modern medical management, which can intuitively and vividly deliver information to patients and obtain effective feedback, enhance the efficiency of doctor-patient communication, and improve the enthusiasm of patients to participate in the perioperative management, which is especially suitable for the popularization and application of patient-oriented prehabilitation, and reduces the waste of medical human resources and economic burden. Under the normalization of epidemic prevention and control, the Internet and online diagnosis and treatment will provide a more effective way for preoperative prehabilitation.

“Internet +” perioperative management is in line with the trend of China's medical service innovation and development. The application of the Internet in the field of healthcare is becoming more and more widespread, and has also been strongly supported and advocated by the state. 2016, the CPC Central Committee

and State Council issued the “Healthy China 2030” planning program, in 2017, the General Office of the State Council issued the “China's medium- and long-term plan for the prevention and treatment of chronic diseases (2017-2025),” and The Opinions on Promoting the Development of “Internet+Medical Health” issued by the General Office of the State Council in 2018, all emphasize the construction of a health information service system, innovation, exploration and improvement of the “Internet+” medical and health service system, the development of telemedicine, health consultation and health management services, and the enhancement of clinical and health care services. consulting, health management services, and strengthen the integration, sharing and application of clinical and scientific research data [10-11].

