measurement of the 6-min walking distance (6MWD). At the same time, it includes the self-measurement of 6min walking distance (6MWD), and patients can complete the self-measurement of 6MWD according to the prompts of the application;

- 6) Implementation and feedback function: It can realize the guidance and adjustment of prehabilitation strategy after reassessment; and set up functions such as daily reminder and prehabilitation activity record.

3.2 To conduct a study on the impact of short-term internet + wearable device-based home-based multilink prehabilitation management on preoperative functional status and prognosis of patients undergoing VATS surgery compared to the traditional model.

A prospective randomized controlled single-blind clinical trial. 64 patients with diagnosed lung occupations intended for VATS surgery were to be included. They were randomized into the “Internet+” group and the traditional prehabilitation control group.

- 1) Sixty-four adults aged ≤ 75 years; suspected lung cancer intended for VATS lobectomy/sublobar resection were selected for the study.
- 2) Prehabilitation intervention: Both groups underwent individualized home-based multimodal prehabilitation strategies, and the timing of the prehabilitation intervention was about 2 weeks from the time the doctor and the patient jointly decided to have the surgery to 1 day before the surgery. The content of prehabilitation included smoking cessation, aerobic training,

anaerobic exercise, nutritional optimization and psychological support. The "Internet+" group used the management mode of online application + wearable devices; the traditional prehabilitation group used the traditional management mode of preoperative preaching + paper records + regular weekly reminders from medical staff.

- 3) Study endpoints: The follow-up period was from the time when the surgeon and the patient decided to operate to 30 days after the operation. The 6MWD was used as the primary assessment of perioperative functional status and the primary endpoint of the study, and patients were evaluated at enrollment, before surgery, and 30 days after surgery. Secondary endpoints included: length of hospitalization, postoperative complications, and pulmonary function, as well as multiple perioperative functional status scores. The feasibility of "Internet Plus" management and patient implementation were assessed.

4. Sample size and statistical methods

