The design of this study was a prospective randomized controlled study, and the sample size of this study was based on the difference in the primary outcome 6-minute walk test distance (6MWD) between the two groups at 30 days postoperatively. It is currently recognized that a difference of 30m in a patient's 6MWD is clinically significant. According to the pre-test of the research team, the standard deviation of the 6MWD was 40 m. The probability of class I error was calculated as 0.05 bilaterally and $\beta=0.2$ to obtain 29 patients in each of the two groups, and 32 patients in each of the two groups were taken to account for the

10% shedding of medical records.

The statistical software for this study was in R language (R Foundation for Statistical Computing, Vienna, Austria; version 3.5.2). Measurements were expressed as mean \pm standard deviation or quartiles, depending on the distribution, and counts were expressed as frequencies. In this study, for the primary outcome 6MWD, as well as for the WHODAS 2.0, and the HADS psychological scores, repeated measurements were taken at different time points in the same patient. Considering the correlation between multiple measurements, a linear mixed-effects model was developed in this study to analyze the effect of the intervention. Intervention factors, time points as categorical variables, and interactions between intervention factors and time as fixed effects were included in the model. When there was no evidence in the model suggesting an interaction between the intervention and time, it was removed from the model to estimate the effect of the intervention on the primary outcome at all time points and the effect of time on the primary outcome. Also, given the potential bias of patients missing visits, we will perform sensitivity analyses of the worst measurements for all patients with missing 6MWD data and determine whether missing data have an impact on the analysis of the primary outcome. For other single-measure secondary outcomes, group comparisons were performed using the paired t test for measures that satisfied normality and the nonparametric Mann-Whitney U test for measures that did not satisfy normality. Count data were expressed as frequencies, and intergroup comparisons were performed using the χ^2 test. The test level was $\alpha=0.05$. A statistically significant difference was defined as a two-sided $P<0.05$.

5. Patient inclusion and exclusion criteria

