5.1 Inclusion

- 1) Age: 18-75 years;
- 2) 64 adults with suspected lung cancer proposed for VATS lobectomy/sublobar resection.

5.2 exclusion:

- 1) Patient refusal;
- 2) ASA classification III or higher;
- 3) Pre-neoadjuvant chemotherapy;
- 4) Inability to cooperate (psychiatric abnormalities, impaired consciousness, mental retardation);
- 5) Comorbidities cannot tolerate home rehabilitation or functional motor examination;
- 6) Inability to use a smartphone or read Chinese;
- 7) Average weekly moderate-intensity/high-intensity exercise of >90min/>60min.

6. Research process

- 1) Patients were assessed for enrollment criteria at the time of their initial outpatient visit and decision to proceed with surgery. After obtaining informed consent from the patients, basic information (basic, past medical history, metabolic equivalents, etc.), smoking status, ASA classification, metabolic equivalents, 6MWD, lung function, grip strength, NRS 2002 nutritional risk screening, HADS and WHODAS 2.0 scores were collected
- 2) Both groups were given routine preoperative anesthesia clinic visits and

guidance, and a short-term home multimodal prehabilitation intervention strategy of about 2 weeks, including smoking cessation, aerobic exercise, impedance training, respiratory exercise, nutritional guidance, whey protein powder supplementation and psychological support. Elastic bands, whey protein powder and respiratory trainers were distributed to patients in both groups.

The “Internet+” team trained patients on the online application of the “Preoperative Family Prehabilitation Program” . The patients used the online application for prehabilitation, followed the exercises, and used the sports bracelet as a wearable device to adjust the exercise intensity and record the exercise time.

Patients in the traditional group were issued a portable finger oxygenator to assist in the completion of exercises, as well as a Pre-Rehabilitation Manual and Completion Record Form, which patients were instructed to fill out daily, and patients were followed up twice a week.

Comprehensive reference to previous studies and prior research by the group, combined with patient execution, to propose a concise and easy-to-follow exercise program:

- i) Tobacco and alcohol cessation
- ii) Aerobic exercise

Aerobic exercise is the core of exercise training in a way that consists of two steps, the first step being a 5-minute warm-up process. The second

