[figure not shown]
performed twice a day for 10 minutes each time, and respiratory exercises include balloon blowing, three-ball instrument, respiratory trainer, and active cycle breathing techniques. Individualized protocols are developed based on the patient's underlying respiratory function and tolerance.

v) Dietary and psychological adjustments

The European Society of Clinical Nutrition and Metabolism recommends a daily protein intake of 1.2g/kg-1.5g/kg (ideal weight for obese patients) for surgical patients. Patients are advised to change unhealthy dietary habits, especially high-calorie and high-fat diets, and increase the intake of vegetables, fruits and high-quality proteins (fish, chicken breast and other lean meats, milk, eggs, soybeans) as appropriate. In addition, patients are advised to supplement high-quality protein, such as whey protein powder, one hour before exercise every day to better promote muscle synthesis according to their individual conditions. Encourage patients to perform self-psychological adjustment and listen to relaxing music to sleep before bedtime every day.

The 6MWD at 30 days postoperatively was used as the primary assessment of functional status and the primary endpoint of the study (enrollment, preoperative and 30 d postoperative); secondary endpoints included pulmonary function, length of hospital stay, ICU stay, postoperative complications, and hospitalization costs, and the HADS assessed perioperative psychosocial, the QoR-15 scale assessed

near-term prognosis, and the WHODAS-2.0 scale assessed mid-term prognosis.

7. Research quality control

- 1) All 6-minute walk tests were measured by a unified person, conducted in accordance with international standard procedures and equipped with first-aid

medicines, so that patients could be dealt with in a timely manner if they felt unwell or needed to take a rest;

2) The whey protein powder provided free of charge to the patients was selected from "Nerishi" isolate whey protein powder through the Nutrition Department of the hospital, taking into consideration the purity, purification method, safety, taste and other issues;

3) For patients in the traditional prehabilitation group who have no wearable devices, patients are provided with free finger oxygen meters to facilitate patients to record their heart rate during aerobic exercise, adjust the intensity of exercise, and ensure the safety and effectiveness of exercise;

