4) provide patients with free three-ball instrument respiratory trainer, resistance respiratory trainer and elastic band exercise equipment without safety problems.

The three-ball instrument respiratory trainer and our hospital unified sale for the same manufacturer and supplier products;

5) Full-process supervision of patients' prehabilitation implementation, including daily short message reminders and study log-in records for patients in the Internet + wearable device group, and 2 weekly SMS/WeChat or telephone follow-up visits for patients in the traditional group to ensure their implementation;

6) Data are entered by two persons, and data consistency test is conducted to clean and screen the data to avoid entry errors.

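### Hospitalization cost can support only an inpatient conclusion, and neither test named in Section 4 suits a between-arm comparison of mean cost

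*Combined protocol and SAP*

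**What the plan says.** **Endpoint.** The last paragraph of Section 6 lists "length of hospital stay, ICU stay, postoperative complications, and hospitalization costs" as secondary endpoints. Cost is not defined further. Section 3.2, item 3, gives another list with no cost item: "Secondary endpoints included: length of hospitalization, postoperative complications, and pulmonary function, as well as multiple perioperative functional status scores".

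**Background.** The introduction says of Internet-based medical services in general that this mode of care "reduces the waste of medical human resources and economic burden".

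**Where the arms differ.** Section 3.2, item 2, times the home programme "from the time the doctor and the patient jointly decided to have the surgery to 1 day before the surgery", about two weeks. Both arms get the same kinds of prehabilitation content. In Section 6 the Internet+ arm is trained on the application and "used the sports bracelet as a wearable device to adjust the exercise intensity and record the exercise time"; the traditional arm gets a finger oximeter, a manual and a record form. Section 7, item 5, adds daily messages with log-in records on the Internet+ side; the control arm instead has "2 weekly SMS/WeChat or telephone follow-up visits for patients in the traditional group".

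**Analysis.** No cost analysis is described, so cost falls under Section 4's rule for secondary outcomes measured once: a paired t test if normal, and "the nonparametric Mann-Whitney U test for measures that did not satisfy normality". Section 4 also summarises measurements by mean and standard deviation or by quartiles, according to distribution.

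**The concern.** There are two issues.

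1. **Scope.** The management modes use different resources at home before admission, while the only cost endpoint is named for the hospital stay. If a cost result were later read together with the background remark, it could be taken as evidence on staff and device resources that were not measured.

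2. **Analysis.** A cost comparison is normally about the arithmetic mean, because the mean times the number of patients gives the total spent. Hospital costs are usually skewed, so the Mann-Whitney branch is the likely one. That test compares ranks, and under Section 4 a skewed cost would be summarised by quartiles, so the mean might not be reported at all. The normal branch names a test for paired data, which this trial does not have.

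At stake is the reading of one secondary endpoint. The 6MWD analysis does not depend on it.

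**Working it through.** **1. The plan's own figure.** The only sized endpoint is 6MWD: difference 30 m, SD 40 m, two-sided alpha 0.05, power 0.80 (Section 4).

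- Normal approximation: n = 2 × (1.96 + 0.84)² × 40² / 30² ≈ 27.9, so 28 per arm. The t-based solution is 28.9, so 29, as stated.
- Dropout: 28 / 0.9 = 31.1, so 32; 29 × 1.1 = 31.9, so 32; 29 / 0.9 = 32.2, so 33.

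The stated 29 and 32 reproduce, but do not bear on cost.

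**2. Precision for cost at this size.** Detectable standardised difference at 80% power: d = (1.96 + 0.84) × √(2/n), which is 0.74 for n = 29 and 0.70 for n = 32. The documents give no cost mean or SD, so the coefficient of variation (CV) is assumed:

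| Assumed CV | Detectable difference, % of mean cost |
|---|---|
| 0.2 | 14 to 15 |
| 0.5 | 35 to 37 |
| 1.0 | 70 to 74 |

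Any method will give a wide interval.

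**3. What the tests do with skewed cost.** All inputs here are assumptions: log-normal costs, 32 per arm, 4,000 simulated trials per scenario (at least 1,000 for bootstrap results).

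*A few costly stays.* Log-SD 0.25 in both arms; in one arm 10% of patients cost three times as much. Mean ratio = 0.9 × 1 + 0.1 × 3 = 1.20. Ranges are over repeat runs.

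| Method | Detects the 20% difference | 95% CI coverage |
|---|---|---|
| Mann-Whitney | 10% to 11% | no mean estimated |
| Welch t | 25% to 26% | about 92% |
| Percentile bootstrap | 37% to 40% | about 90% to 91% |
| Studentized bootstrap | about 43% | about 92% |

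*Equal medians, unequal spread.* A log-normal mean is median × exp(σ²/2).

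- Log-SD 0.3 vs 0.6: mean ratio exp((0.36 − 0.09)/2) = 1.145. Mann-Whitney rejects in 6.2%, Welch in 12.6%.
- Log-SD 0.3 vs 0.9: mean ratio exp((0.81 − 0.09)/2) = 1.433. Mann-Whitney rejects in 7.5%, Welch in 26.0%.

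*Equal means, unequal spread.* Median ratios are exp(−0.135) = 0.874 and exp(−0.36) = 0.698. Mann-Whitney rejects in about 20% and 54%, although mean cost does not differ.

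With log-SD 0.3 in both arms and no difference, Mann-Whitney rejects in 4.7%. The problem comes from differing distribution shapes, not from a faulty test.

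**4. Pre-admission contacts.** Section 7 gives two control contacts a week: 2 × 2 weeks × 32 = about 128. Section 3.2 speaks of weekly reminders; read as once a week, that is 1 × 2 × 32 = about 64. The passages need reconciling. On the other side stand 32 application trainings and 32 bracelets. No section plans to record staff minutes or the cost of devices or the application.

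**The case against.** **The saving is not a study claim.** A reader might infer that the trial sets out to show that the application saves staff and money, and that its cost endpoint fails that test. The documents do not support this. The remark is a background statement about a mode of care; none of the four purposes in Section 2 concerns cost or staffing, and Section 3.2 compares functional status and prognosis. A full delivery-cost evaluation would be an addition, not the repair of a defect.

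**Inpatient cost answers a valid question.** A reader might also infer that it says nothing about resources. That is too strong: listed beside length of stay, ICU stay and complications, it captures downstream effects, and shorter stays are real savings.

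**The contact contrast is partly assumed.** It is tempting to set about 128 control contacts against none in the Internet+ arm. Section 3.1 lists a daily reminder as an application function, but the documents do not say whether the messages in Section 7 are automated, and Section 7 describes supervision in both arms. Log-in records and a fixed contact schedule would also allow a rough reconstruction later, though not of actual minutes.

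**The analysis point is conditional and generic.** Mann-Whitney applies only if cost fails normality, the simulation inputs are assumed, and the alternatives still miss the 20% difference in more than half of trials. Paired may be a slip for an independent-samples test.

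The first three objections stand and confine the scope issue to a limit on interpretation. The fourth lowers the weight of the analysis issue but does not remove it: the text as written gives no suitable between-arm estimate of mean cost with a confidence interval in either branch.

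**Conclusion.** The point holds in a limited form. Hospitalization cost, read in the ordinary way as inpatient cost, cannot by itself support a statement that the Internet+ mode saves management resources; it can support a statement about inpatient cost. That reading is an inference, because the plan does not define the term.

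Section 4 leaves cost without a suitable analysis. The skewed branch does not address the mean: in the illustrations Mann-Whitney detects a 20% higher mean in only 10% to 11% of trials and rejects in 20% to 54% when means are equal. The normal branch names a test that does not fit independent arms. The size of the error in this trial cannot be stated without cost data.

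The consequence is minor: one unpowered secondary endpoint, with no effect on the primary endpoint or the stated purposes. It merits correction because the correction costs almost nothing.

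**What to change.** 1. In Section 4, give cost its own rule in place of both branches: the between-arm difference in arithmetic mean with a 95% CI, by Welch or by a bias-corrected or studentized bootstrap. The plain percentile bootstrap is the weaker choice, with coverage of about 90% at 32 per arm in the illustration. Welch and the studentized version reached about 92%, so the interval should be called approximate.
2. Define hospitalization cost (components, perspective, time window) and align the secondary endpoint lists in Sections 3.2 and 6.
3. Label the result an imprecise secondary estimate and limit any cost conclusion to inpatient cost.
4. Optional, only if a management-resource conclusion is wanted: staff already making the contacts log minutes per contact and per application training in both arms, and unit costs of devices, application and printed material are added.

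Items 1 to 3 cost a few lines of text and one short analysis. Item 4 adds a slight clerical burden, and its interval will also be wide.
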